### 2.1.1.4 Unscheduled visits

For unscheduled visits, the analysis visits will be derived with windowing where appropriate (e.g., Visit  $3 \pm 3$  days) as per the protocol. For scheduled visits, the analysis visits will be the actual (reported) visit number.

Data collected at unscheduled visits will not be used in 'by-visit' tabulations, graphs or analyses unless it can be mapped to a missed scheduled visit with the window specified per the protocol. If multiple unscheduled visits are allocated to the same missed scheduled visit:

- The unscheduled visit closest to the missed scheduled visit will be used
- If there are multiple unscheduled visits with the same distance to the missed scheduled visit, the latest one will be used

For analyses showing abnormalities, data from unscheduled visits will be considered individually, without mapping to a main visit.

For analyses based on all post-baseline values such as averages over a given period summaries of maximum/minimum values, data collected at unscheduled visits will be included.

All data collected at unscheduled visits will be listed.

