### 2.1.1.2 Baseline and post-Baseline

*Baseline* (Day 1) is defined as

- the day following randomization for subjects randomized to untreated control
- the day of successfully receiving GT005 administration for subjects randomized to GT005
- or the latest surgery date for subjects who were randomized to GT005 but failed to receive GT005 administration on the first attempt to surgery (if applicable)

The baseline value for efficacy and safety variables is the last available value (scheduled or unscheduled) collected prior to the date of *Baseline*, or on the date of *Baseline* but prior to the time of GT005 administration for GT005 treatment groups.

All data collected after the date of *Baseline* are defined as post-baseline. The *study day* for a baseline or post-baseline scheduled or unscheduled visit is defined as:

$$\text{Study day} = \begin{cases} (\text{Date of visit}) - (\text{Date of randomization}) & \text{Untreated} \\ (\text{Date of visit}) - (\text{Date of treatment administration}) + 1 & \text{GT005} \end{cases}$$

The *study day* for a scheduled or unscheduled visit before baseline is defined as

$$\text{Study day} = \begin{cases} (\text{Date of visit}) - (\text{Date of randomization}) - 1 & \text{Untreated} \\ (\text{Date of visit}) - (\text{Date of treatment administration}) & \text{GT005} \end{cases}$$

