### **2.1.1.5 Missing baseline and post-baseline data**

Missing baseline data will not be imputed.

Observations with values ‘not done’, ‘not evaluable’, ‘not applicable’ will be treated as missing values.

In case of multiple entries for the same assessment are observed within one visit, the latest assessment value will be used.

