### 5.4 Statistical models

#### 5.4.1 Analysis supporting primary objective(s)

The following MMRM will be used for the primary efficacy endpoint. The model will include the change from baseline in GA area measured by FAF as the dependent variable, GA area at the baseline as the covariate, assessment visit, treatment group, two interaction terms (assessment visit and treatment group, assessment visit and GA area at the baseline) as the fixed effect and participant as a random effect.

For this analysis, the data structure is one record per subject per scheduled visit. The data will include all subjects and have records for all scheduled visits, regardless of whether the assessment was missed or not at a given visit. Missing values will not be imputed and will be passed to the model as missing. The SAS PROC MIXED will be used to perform the analysis.

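### SAP 2.1.1.4 admits unscheduled data by missed visit rather than by missing assessment, so, read literally, an in-window repeat FAF after an attended Week 48 visit stays out of the primary model

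*SAP*

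**What the plan says.** The primary endpoint is change in GA area on FAF from baseline to Week 48 (SAP 2.5.1). The schedules of assessments in the protocol (Tables 1 and 2) give Week 48 a window of 7 days either side.

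Four SAP rules decide which FAF value represents Week 48:

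- **SAP 2.1.1.4, assignment.** "For unscheduled visits, the analysis visits will be derived with windowing where appropriate". "For scheduled visits, the analysis visits will be the actual (reported) visit number".
- **SAP 2.1.1.4, use.** Unscheduled data do not enter by-visit tables, graphs or analyses "unless it can be mapped to a missed scheduled visit with the window specified per the protocol". If several unscheduled visits qualify, the closest is taken, and on a tie the latest. They do enter analyses based on all post-baseline values, and "All data collected at unscheduled visits will be listed".
- **SAP 2.1.1.5.** "Observations with values ‘not done’, ‘not evaluable’, ‘not applicable’ will be treated as missing values". Where one visit holds several entries for the same assessment, the latest is used.
- **SAP 5.4.1.** The dataset has one record per subject per scheduled visit. "Missing values will not be imputed and will be passed to the model as missing".

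For comparison, under SAP 2.1.1.2 the baseline value of a variable "is the last available value (scheduled or unscheduled) collected prior to the date of" Baseline. That rule works variable by variable and draws on both kinds of visit.

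**The concern.** The rule asks whether the visit was missed, when what matters for the analysis is whether the measurement is missing. The two differ when a subject attends and one test fails. The subject is present, other assessments are done, the FAF cannot be graded, and the site images the eye again a few days later. If that return is recorded as an unscheduled visit, there is no missed scheduled visit for it to map to. A subject who did not attend at all, and had the same image on the same day, would have it used.

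Nothing in the SAP explains why attendance for other tests should make a valid FAF value unusable. What is at stake is an observed, centrally graded value of the primary endpoint, replaced by reliance on missing at random. The rule is general, so it also governs BCVA, LLD, MNRead, FRI and VFQ-25. Apart from BCVA, these are summarised from observed data by visit (SAP 2.6.2), so there no model recovers anything.

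**Working it through.** **Step 1. Apply the rules to three records.** In each, a gradable FAF is obtained within 7 days of the scheduled Week 48 date.

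| Record | Week 48 visit | How the gradable image is recorded | Rule that decides | Week 48 GA area in the MMRM |
|---|---|---|---|---|
| A | Skipped | Unscheduled visit | 2.1.1.4: maps to a missed visit | Used |
| B | Attended, FAF not evaluable | Unscheduled visit | 2.1.1.4: visit not missed; 2.1.1.5: scheduled FAF missing | Missing, read literally |
| C | Attended, FAF not evaluable | Second entry under Week 48 | 2.1.1.5: latest entry | Used |

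A and B differ only in whether the subject attended. B and C differ only in how the site files the image.

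**Step 2. Check the window.** It runs from the scheduled date, not from the date attended. A repeat five days after attendance is in window only if the subject attended no later than 7 − 5 = 2 days after the scheduled date. Record B therefore needs an early enough attendance or a quick repeat.

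**Step 3. Bound the size.** The plan gives no figure for this loss, so there is none to reproduce. Inputs from the documents:

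- total about 202, including about 10 on high dose (protocol 9.1), so low dose plus control is 202 − 10 = 192
- 2:1 allocation, taken as 128 low dose and 64 control
- SD 1.3 mm² (protocol 9.1)
- 12% without a Week 48 value, the upper end of the 10–12% in the protocol synopsis

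Assumed, because no document gives it: a share *q* of the remaining Week 48 values is lost in the manner of record B. The share is equal in both arms, and other visits recover nothing.

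Before loss, control is 64 × 0.88 = 56.3 and low dose 128 × 0.88 = 112.6, total 169.0.

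SE = 1.3 × √(1/56.3 + 1/112.6) = 0.2122 mm².

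With equal loss the SE is multiplied by 1/√(1 − *q*). The half-width of the 90% interval is 1.645 × SE.

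| *q* | Values lost (169.0 × *q*) | SE (mm²) | SE increase | 90% CI half-width (mm²) |
|---|---|---|---|---|
| 0 | 0 | 0.2122 | – | 0.349 |
| 2% | 3.4 | 0.2143 | 1.0% | 0.353 |
| 5% | 8.4 | 0.2177 | 2.6% | 0.358 |
| 10% (outer case) | 16.9 | 0.2236 | 5.4% | 0.368 |

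For a given *q*, the SE increases are upper bounds, because the MMRM uses each subject's other FAF visits. The counts rest on planned enrolment, and the SAP was written for a study being stopped early, so they may differ. The percentage increase depends only on *q*.

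*q* is a joint rate: the visit attended, FAF not done or not gradable, FAF repeated, repeat gradable, repeat in window, and repeat recorded as unscheduled.

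**The case against.** The best answer is that the text does not force the literal reading. *Missed* is not defined, and nothing says that the whole visit must be missed. The windowing sentence in SAP 2.1.1.4 first gives unscheduled visits an analysis visit. SAP 5.4.1, which governs the primary model, speaks of an assessment being missed at a visit. A programmer could read the rule per assessment. The latest-entry rule would also rescue a repeat filed under Week 48. Protocol 6.1.15 describes unscheduled visits as clinically indicated, and a technical re-image may not be one. The Central Imaging Manual, to which FAF specifications are deferred, may settle the filing but is not among the documents.

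Much of this stands: the loss is conditional, and no passage addresses a repeat image after a failed one. It does not remove the point. The restriction on use follows the windowing sentence and limits it. The tie-breaks select visits, not assessments. The wording in 5.4.1 shows that the SAP can distinguish a missed assessment from a missed visit, and in 2.1.1.4 it named the visit. If the outcome depends on how a site files the image, that is itself a reason to settle the rule.

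The baseline rule is a comparison, not a contradiction: choosing the last value before Day 1 is a different task from mapping to visits.

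A reader might also infer that the loss would fall mainly on GT005 eyes, since only they have the surgery and the protocol cites cataract extraction in about 40% of patients over the two years after vitrectomy. The documents do not support this. The rule costs data only when the repeat is gradable within days, and a lens opacity would not be expected to clear in that time. The 40% is a two-year surgery figure, not a Week 48 image-failure rate. Clinically significant cataract that may require surgery in the study eye is an exclusion criterion, and protocol 1.6.1.2 places any cataract surgery at least 4 weeks before Week 48.

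**Conclusion.** The point holds in a limited form. Read literally, SAP 2.1.1.4 treats a gradable in-window repeat FAF worse when the subject attended Week 48 than when the subject stayed away. This applies when the repeat is recorded as an unscheduled visit, and not when it is entered under Week 48.

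It would be too strong to say that the plan discards primary-endpoint data. The result is still listed and enters analyses of all post-baseline values. The subject remains in the MMRM through other visits, and only the observed Week 48 value is absent.

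The effect is probably small. At an assumed 2–5% it is about 3 to 8 values and at most a 1–2.6% larger standard error for the low-dose comparison, given equal loss by arm and planned numbers. The true rate is unknown, no imbalance is shown, and the protocol plans no inferential testing. This is a low-severity improvement, worth making because the per-assessment rule is better and costs almost nothing.

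**What to change.** In SAP 2.1.1.4, replace the condition in "unless it can be mapped to a missed scheduled visit with the window specified per the protocol" with one based on the assessment: *mapped, within the protocol window, to a scheduled visit at which that assessment is missing, not done or not evaluable*. Apply the existing closest-then-latest tie-breaks separately for each assessment, and state that the window is counted from the scheduled date. An evaluable value from the scheduled visit then keeps precedence, and records A, B and C are treated alike.

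The cost is one or two sentences in the SAP and a merge by parameter instead of by visit in the dataset specification. No new data are needed.

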### **2.1.1.5 Missing baseline and post-baseline data**

Missing baseline data will not be imputed.

Observations with values ‘not done’, ‘not evaluable’, ‘not applicable’ will be treated as missing values.

In case of multiple entries for the same assessment are observed within one visit, the latest assessment value will be used.

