## 7.4 Safety

### 7.4.1 Vital Signs

Vital signs including heart rate, temperature, and blood pressure will be measured. Blood pressure (systolic and diastolic) is to be measured in triplicate after 5 minutes rest in a sitting position. The same method should be used throughout the study. Heart rate will be assessed as a single measurement.

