### 9.4.3 Safety Assessments

Safety evaluations include AEs, ophthalmic imaging and examinations, BCVA (ETDRS) score (assessed as both an efficacy and safety endpoint), vital signs, laboratory safety (biochemistry and haematology), [REDACTED]

AEs will be summarised in two parts: systemic events and ocular events. For systemic events, data will be displayed according to treatment received (low dose [REDACTED] vg, high dose [REDACTED] vg, and untreated). Ocular events will be displayed according to treatment allocation (including GT005 dose group) and study eye (study eye and contralateral eye).

All AEs (overall, by seriousness, by severity, by relationship) recorded throughout the study will be reported following classification according to the Medical Dictionary for Regulatory Activities (MedDRA) dictionary. [REDACTED]

Systemic safety evaluations including vital signs, laboratory safety, [REDACTED] will be summarised over time by dose and overall.

Ocular safety evaluations including ophthalmic examination variables (cataract grading, intra-ocular pressure, etc.) and BCVA scores will be summarised in the same manner as ocular efficacy variables, dependant on data type.

[REDACTED]  
[REDACTED]  
[REDACTED]  
[REDACTED]  
[REDACTED].

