### 2.7.5.2 Vital signs

A listing of subjects satisfying at least one criterion in [Table 2-2](#) at any visit will be presented.

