**Table 2-2 Clinically notable vital signs**

Variable	Category	Critical values
Systolic blood pressure (mmHg)	High	Either >180 with an increase from baseline >30 or >200 absolute
	Low	Either <90 with a decrease from baseline >30 or <75 absolute
Diastolic blood pressure (mmHg)	High	Either >105 with an increase from baseline >20 or >115 absolute
	Low	Either <50 with a decrease from baseline > 20 or <40 absolute
Pulse rate (bpm)	High	Either >120 with an increase from baseline of >25 or > 130 absolute
	Low	Either <50 with a decrease from baseline >30 or <40 absolute

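### The SAP does not say how triplicate blood pressure is combined, and its only rule for several entries in a visit would use one of the three readings

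*SAP*

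**What the plan says.** Protocol 7.4.1 states: "Blood pressure (systolic and diastolic) is to be measured in triplicate after 5 minutes rest in a sitting position". For pulse the same section states: "Heart rate will be assessed as a single measurement". Only blood pressure is therefore replicated by design.

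For several values within one visit, SAP 2.1.1.5 gives a single rule: "In case of multiple entries for the same assessment are observed within one visit, the latest assessment value will be used". It makes no exception for planned replicates. The baseline definition in SAP 2.1.1.2 points the same way: "The baseline value for efficacy and safety variables is the last available value (scheduled or unscheduled) collected prior to the date of" Baseline.

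For vital signs, SAP 2.7.5.2 promises one output, which begins "A listing of subjects satisfying at least one criterion in" Table 2-2, with the criteria applied at any visit. The high systolic criterion is "Either >180 with an increase from baseline >30 or >200 absolute" and the high diastolic criterion is "Either >105 with an increase from baseline >20 or >115 absolute". Neither the section nor the table names the reading, or the combination of readings, to be compared with these limits.

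Protocol 9.4.3 says that systemic safety evaluations, vital signs among them, "will be summarised over time by dose and overall".

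**The concern.** Readings are taken in triplicate so that they can be averaged and the short-term measurement error reduced. A programmer who applies SAP 2.1.1.2 and 2.1.1.5 literally to separately stored readings would take the third at baseline and the third at every later visit, and would lose that benefit. The extra error can put a subject on the notable list by chance. It can also leave off a subject whose earlier readings in the visit crossed a limit.

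A smaller, separate matter is that the protocol plans a summary over time while the SAP specifies only a listing. SAP section 4, which records departures from the protocol's analyses, does not mention this.

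**Working it through.** The documents contain no figure that depends on this rule, so there is nothing of the plan's own to reproduce.

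**1. Does any other text override the rule?** SAP 2.1.1.4 has a special provision for analyses of abnormalities, but it concerns unscheduled visits, not replicates within a visit. SAP 2.7.5.2 and Table 2-2 are silent. No readable text in either document averages the three readings.

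**2. Within-visit error.** Let s be the within-visit SD, with independent errors.
- One visit: last reading s; mean of three s/√3.
- Change from baseline: last readings s√2; means of three s√(2/3).
- Ratio: √3 = 1.73 in SD, 3 in variance, whatever s is.

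**3. Whole variability of a change.** Change between visits also carries between-visit variation, with SD b, which averaging within a visit does not reduce.
- Last readings: √(2(b² + s²)). Means of three: √(2(b² + s²/3)).
- The documents give neither b nor s. Assume b = 10 mmHg for systolic pressure.

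| s (assumed) | Last reading | Mean of three | Excess SD |
|---|---|---|---|
| 4 | √(2 × 116) = 15.2 | √(2 × 105.3) = 14.5 | 5% |
| 8 | √(2 × 164) = 18.1 | √(2 × 121.3) = 15.6 | 16% |

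**4. Effect on the listing.** All high and low blood-pressure criteria in Table 2-2 were simulated with 400,000 subjects per scenario and no treatment effect. The distributions are assumptions:
- systolic: mean 138, between-subject SD 17, between-visit SD 10, s = 3, 5 or 8 mmHg;
- diastolic: mean 78, between-subject SD 10, between-visit SD 6, s = 3, 5 or 6 mmHg.

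The visit numbers come from protocol Tables 1 and 2 and section 6.1. GT005 subjects have vital signs at seven post-baseline visits (Day 2, Weeks 1, 5, 24, 48, 72, 96) and controls at four (Weeks 24, 48, 72, 96).

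| Subjects listed | Last, s = 5 | Mean, s = 5 | Last, range over s | Mean, range over s |
|---|---|---|---|---|
| Systolic, control | 2.2% | 1.6% | 1.6–3.8% | 1.4–2.0% |
| Systolic, GT005 | 3.5% | 2.5% | 2.5–6.1% | 2.2–3.2% |
| Diastolic, control | 3.1% | 1.4% | 1.5–4.5% | 1.1–1.7% |
| Diastolic, GT005 | 4.9% | 2.3% | 2.4–7.1% | 1.7–2.9% |

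Across scenarios the last-reading rule lists about 1.1 times (1.57/1.38) to 2.6 times (4.46/1.73) as many subjects as the mean.

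Even with means of three, GT005 shows more listed subjects than control although no effect was simulated. That gap comes from seven chances to be flagged against four.

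**5. The over-time summary.** Protocol 9.4.3 plans it. SAP 2.7.5.2 specifies only the listing. SAP section 4 records the removal of the Week 48 interim analysis and the safety set, the simpler estimand, the change to MMRM and the dropped subgroup, but nothing about vital signs.

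**The case against.** **The rule may not be meant for triplicates.** It sits under a missing-data heading and may have been written for unplanned repeat entries. The documents also do not show whether the eCRF holds three readings or one average; if it holds one, the rule has no effect. Both points stand, so use of the third reading alone is what the SAP implies if readings are stored separately, not an established fact. They do not remove the gap: the SAP neither limits the rule nor says how the triplicate is combined.

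**The 1.73 ratio invites over-reading.** A reader might infer 73% more noise against the 30 mmHg systolic and 20 mmHg diastolic change limits. The documents do not support that. The ratio covers within-visit error only, and each of those change limits applies together with an absolute limit (above 180 or 105 on the high side).

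**A blood-pressure effect could still be seen.** A reader might infer that none could be judged by arm. SAP 2.7 presents all listings and tables by treatment group, so listed subjects can be counted, and section 2.7.1 tabulates non-ocular adverse events by arm. Nor can the point rest on the corticosteroid regimen, whose details are blacked out; the readable risk text speaks of periocular or topical steroids.

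**The over-time summary may still be produced.** SAP 2.1 describes summaries of continuous data by treatment group unless otherwise specified, and section 2.7.4 excludes by-visit tables for laboratory data only. This softens the point, but a general format statement does not commit the sponsor to a vital-sign table, and section 2.7.5.2 names none.

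**Little depends on it.** The study is being terminated after a futility analysis. This is fair and limits the importance.

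**Conclusion.** The point holds as a minor gap in the SAP. As written, and provided the three readings are stored separately, one of three is used at baseline and at each visit. Given independent errors, within-visit error variance is then three times that of the triplicate mean. The 5% to 16% rise in the SD of change, and the simulated listing rates, rest on assumed SDs and show scale only. The consequence is confined to the listing of clinically notable vital signs; no efficacy result, power or alpha figure is touched.

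The mismatch with protocol 9.4.3 also holds in a limited form: the SAP's vital-sign section specifies less than the protocol planned, and section 4 does not record the difference. It does not depend on how the readings are stored.

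**What to change.** 1. In SAP 2.1.1.5, state that for planned triplicate blood pressure the mean of the available readings is the visit value and the baseline value, and limit the latest-value rule to unplanned repeat entries.
2. Provide the by-visit vital-sign summary planned in protocol 9.4.3, or record its removal in SAP section 4.
3. If the number and percentage of subjects per arm meeting the Table 2-2 criteria are added, restrict the count to the visits common to both schedules (Weeks 24, 48, 72 and 96), or footnote the unequal number of visits (seven under GT005, four under control). An unrestricted count would tend to look worse for GT005 with no true difference.

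The cost is one derivation sentence and a small amount of extra table work.

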### **2.1.1.6 Alternative GA medications or therapies**

Avacincaptad pegol (Izervay) and pegcetacoplan (Syfovre) via intravitreal injection are Food and Drug Administration approved treatments for GA and are permittable alternative GA treatments in this study.

## **2.2 Analysis sets**

The **All-Enrolled Set** includes all patients who signed informed consent. This analysis set will be used to summarize subject disposition.

The **Full Analysis Set (FAS)** will include all subjects who are randomized to GT005 or untreated control. The FAS will be used for the analysis of efficacy and safety data.

The number and percentage of subjects within each of the above analysis sets will be summarized.

